9.1.4 End of Treatment

Subjects discontinuing treatment prior to week 52 for any reason (see Section [8.1](#)) will be asked to complete an End of Treatment visit within a window of \pm 7 days of the next regularly scheduled visit after the last dose of efavaleukin alfa, consisting of all assessments included in the week 52 visit according to the Schedule of Activities (see [Table 2-2](#)). If the End of Treatment visit for a subject occurs $<$ 7 days after a progressive

disease visit, then the procedures completed at the End of Treatment visit should only be those NOT performed at the progressive disease visit.

For phase 1b subjects participating in the extended dosing period, subjects discontinuing treatment prior to week **102** or week **103** will be asked to complete the EOET visit within a window of + 7 days of the next regularly scheduled visit after the last dose of efavaleukin alfa, consisting of all assessments included in week **104** visit according to the Schedule of Activities (see [Table 2-3](#)). Subjects continuing treatment after week **104** but discontinuing treatment before week **258** (Q2W dosing) or week **259** (QW dosing) will be asked to complete an EOET visit within a window of \pm 7 days of the next regularly scheduled visit after the last dose of efavaleukin alfa, consisting of all assessments included in the week **260** visit according to the Schedule of Activities (see [Table 2-6](#)). If the EOET visit for a subject occurs < 7 days after a progressive disease visit, then the procedures completed at the EOET visit should only be those NOT performed at the progressive disease visit.

9.1.5 Safety Follow-up/End of Study

Upon completion of the treatment period or permanent discontinuation from the study treatment for any reason, a safety follow-up visit will be performed approximately 6 weeks (\pm 3 days) after the last dose of efavaleukin alfa as described in the Schedule of Activities (see [Table 2-1](#), [Table 2-2](#), [Table 2-3](#), [Table 2-4](#), [Table 2-5](#), [Table 2-6](#), [Table 2-7](#), and [Table 2-8](#)). Women of childbearing potential will be required to complete a pregnancy test at this visit.

9.2 Description of General Study Assessments and Procedures

The sections below provide a description of the individual study procedures for required time points. These assessments apply to subjects in both phase 1b and [REDACTED] unless otherwise indicated.

9.2.1 General Assessments

9.2.1.1 Informed Consent

All subjects must sign and personally date the IRB/IEC approved informed consent before any study-specific procedures are performed for both the phase 1b and [REDACTED] portions of the study.

9.2.1.2 Demographics

Demographic data including sex, age, race, and ethnicity will be collected in order to study their possible association with subject safety and treatment effectiveness.

Additionally, demographic data will be used to study the impact of biomarker variability and PK of efavaleukin alfa.

9.2.1.3 Medical History

The Investigator or designee will collect complete medical and surgical history within 5 years prior to enrollment. Medical history will include information on the subject's concurrent medical conditions. Record all findings on the medical history CRF. In addition to the medical history above, cGVHD history must date back to the original diagnosis. The current severity will be collected for each condition that has not resolved.

9.2.1.4 GVHD Staging Evaluation

The clinician will complete the GVHD Staging Evaluation form at screening to document that study subjects meet the criteria for moderate-to-severe cGVHD per the 2014 cGVHD NIH Consensus Criteria. [REDACTED] is not required for the Staging Evaluation. Please see [Appendix 9](#) for algorithm for calculation of cGVHD severity.

9.2.1.5 Physical Examination

[figure not shown]
Physical examination will be performed as per standard of care. Physical examination findings should be recorded on the appropriate CRF (eg, medical history, event).

9.2.1.6 Physical Measurements

Height measurement in centimeters without shoes and weight measurement in kilograms and without shoes will be performed at the time points specified in the Schedule of Activities.

9.2.1.7 Substance Abuse History

In phase 1b, obtain a detailed history of prior and/or concurrent use of alcohol, nicotine, and tobacco containing products.

9.2.2 Efficacy Assessments

9.2.2.1 Response Assessment: NIH cGVHD Response Assessment (NIH Form A)

All subjects in the study will have their clinical response assessed using the NIH cGVHD Response assessment (NIH Form A) per the 2014 cGVHD NIH Consensus Criteria

[figure not shown]
(2014 Response Criteria Working Group; Measurement of Therapeutic Response, ASBMT Web site) in accordance with the Schedule of Activities (see [Table 2-1](#), [Table 2-2](#), [Table 2-3](#), [Table 2-4](#), [Table 2-5](#), [Table 2-6](#), [Table 2-7](#), and [Table 2-8](#)).

[figure not shown]
Subjects will undergo repeat detailed assessment of ocular, oral, cutaneous, musculoskeletal, gastrointestinal, hepatic, and pulmonary systems per the [REDACTED]

[REDACTED]
[REDACTED]
[REDACTED]
[REDACTED]

[REDACTED]. Both standard and [REDACTED] response assessments will be captured on the NIH cGVHD Response Assessment (NIH Form A).

[REDACTED]

9.2.3 Safety Assessments

Planned time points for all safety assessments are listed in the Schedule of Activities.

9.2.3.1 Adverse Events and Serious Adverse Events

The method of recording, evaluating, and assessing causality of adverse events and serious adverse events and the procedures for completing and transmitting serious adverse event reports are provided in [Appendix 4](#).

9.2.3.1.1 Time Period and Frequency for Collecting and Reporting Safety Event Information

9.2.3.1.1.1 Disease-related Events

Disease-related events are defined in [Appendix 4](#).

The investigator is responsible for ensuring that all disease-related events observed by the investigator or reported by the subject that occur after the first dose of investigational product through the safety follow-up visit/end of study are recorded using the Event CRF.

All serious disease-related events will be recorded and reported to the sponsor or designee within 24 hours. The investigator will submit any updated serious disease-related event data to the sponsor within 24 hours of it being available.

Disease-related events assessed by the investigator to be more severe than expected and/or related to the investigational product(s)/study treatment/protocol-required therapies, and determined to be serious, must be reported on the Event CRF as serious adverse events and recorded and reported per Section [9.2.3.1.1.3](#) and [Appendix 4](#).

Disease-related events pre-defined for this study are listed in [Appendix 11](#).

9.2.3.1.1.2 Adverse Events

The adverse event grading scale to be used for this study will be the CTCAE version 4.03 and is described in [Appendix 4](#).

The investigator is responsible for ensuring that all adverse events observed by the investigator or reported by the subject that occur from first dose of investigational product through the safety follow-up visit/EOS are reported using the Event CRF.

9.2.3.1.1.3 Serious Adverse Events

The investigator is responsible for ensuring that all serious adverse events observed by the investigator or reported by the subject that occur after signing of the informed consent through safety follow-up visit/EOS are reported using the Event CRF.

All serious adverse events will be collected, recorded and reported to the sponsor or designee within 24 hours, as indicated in [Appendix 4](#). The investigator will submit any updated serious adverse event data to the sponsor within 24 hours of it being available.

The criteria for grade 4 in the CTCAE grading scale differs from the regulatory criteria for serious adverse events. It is left to the investigator's judgment to report these grade 4 abnormalities as serious adverse events.

9.2.3.1.1.4 Serious Adverse Events After the Protocol-required Reporting Period

If the investigator becomes aware of serious adverse events after the protocol-required reporting period (**as defined in Section 9.2.3.1.1.3**) **is complete**, these serious adverse events **will** be reported to Amgen (**regardless of causality**). **The investigator will** report serious adverse events to Amgen within 24 hours following the investigator's **awareness** of the event.

Serious adverse events reported outside of the protocol-required reporting period will be captured within the safety database as clinical trial cases and handled accordingly based on relationship to investigational product.

If further safety related data is needed to fulfill any regulatory reporting requirements for a reportable event, then additional information may need to be collected from the subject's records after the subject ends the study.

9.2.3.1.2 Method of Detecting Adverse Events and Serious Adverse Events

Care will be taken not to introduce bias when detecting adverse events and/or serious adverse events. Open-ended and non-leading verbal questioning of the subject is the preferred method to inquire about adverse event occurrence.

9.2.3.1.3 Follow-up of Adverse Events and Serious Adverse Events

After the initial adverse event/serious adverse event report, the investigator is required to proactively follow each subject at subsequent visits/contacts. All adverse events and serious adverse events will be followed until resolution, stabilization, until the event is otherwise explained, or the subject is lost to follow-up (as defined in Section 8.3).

Further information on follow-up procedures is given in [Appendix 4](#).

All new information for previously reported serious adverse events must be sent to Amgen within 24 hours following knowledge of the new information. If specifically requested, the investigator may need to provide additional follow-up information, such as discharge summaries, medical records, or extracts from the medical records.

Information provided about the serious adverse event must be consistent with that recorded on the Event CRF.

9.2.3.1.4 Regulatory Reporting Requirements for Serious Adverse Events

If subject is permanently withdrawn from protocol-required therapies because of a serious adverse event, this information must be submitted to Amgen.

Prompt notification by the investigator to the sponsor of serious adverse events is essential so that legal obligations and ethical responsibilities towards the safety of subjects and the safety of a study treatment under clinical investigation are met.

The sponsor has a legal responsibility to notify both the local regulatory authority and other regulatory agencies about the safety of a study treatment under clinical investigation. The sponsor will comply with country-specific regulatory requirements relating to safety reporting to the regulatory authority, IRBs/IECs, and investigators.

Individual safety reports must be prepared for suspected unexpected serious adverse reactions (SUSAR) according to local regulatory requirements and sponsor policy and forwarded to investigators as necessary.

An investigator who receives an individual safety report describing a serious adverse event or other specific safety information (eg, summary or listing of serious adverse events) from the sponsor will file it along with the Investigator's Brochure and will notify the IRB/IEC, if appropriate according to local requirements.

9.2.3.1.5 Pregnancy and Lactation

Details of all pregnancies and/or lactation in female subjects and, if indicated, female partners of male subjects will be collected after the start of study treatment and until 6 weeks after receiving the last dose of Amgen investigational product.

If a pregnancy is reported, the investigator is to inform Amgen within 24 hours of learning of the pregnancy and/or lactation and is to follow the procedures outlined in [Appendix 5](#). Amgen Global Patient Safety will follow-up with the investigator regarding additional information that may be requested.

Abnormal pregnancy outcomes (eg, spontaneous abortion, fetal death, stillbirth, congenital anomalies, ectopic pregnancy) are considered serious adverse events.

Further details regarding pregnancy and lactation are provided in [Appendix 5](#).

9.2.3.2 Vital Signs

The following measurements must be performed: Systolic/Diastolic Blood Pressure, Heart Rate, Respiratory Rate, and Temperature. Subject must be in a supine position in a rested and calm state for at least 5 minutes before blood pressure assessments are conducted. If the subject is unable to be in the supine position, the subject should be in most recumbent position as possible. The position selected for a subject should be the same that is used throughout the study and documented on the vital sign CRF. The temperature location selected for a subject should be the same that is used throughout the study and documented on the vital signs CRF. Record all measurements on the vital signs CRF.

9.2.3.3 Electrocardiograms (ECGs)

Single ECGs will be collected at screening and at time points per the Schedule of Activities (see [Table 2-1](#), [Table 2-2](#), [Table 2-3](#), [Table 2-4](#), [Table 2-5](#), **Table 2-6**, [Table 2-7](#), and [Table 2-8](#)).

Subject must be in supine position in a rested and calm state for at least 5 minutes before ECG assessment is conducted. If the subject is unable to be in the supine position, the subject should be in most recumbent position as possible. ECGs should be performed in a standardized method prior to blood draws or other invasive procedures. Each ECG must include the following measurements: QRS, QT, QTc, RR, and PR intervals.

The investigator will review all ECGs. Once signed, the original ECG tracing will be retained with the subject's source documents. At the request of the sponsor, a copy of the original ECG will be made available to Amgen.

Standard ECG machines should be used for all study-related ECG requirements. In certain circumstances Amgen may be able to provide a standard ECG machine if a site is unable to provide one.

9.2.4 Clinical Laboratory Assessments

Refer to [Appendix 2](#) for the list of clinical laboratory tests to be performed and to the Schedule of Activities (see [Table 2-1](#), [Table 2-2](#), [Table 2-3](#), [Table 2-4](#), [Table 2-5](#), **Table 2-6**, [Table 2-7](#), and [Table 2-8](#)) for the timing and frequency.

The investigator is responsible for reviewing laboratory test results and recording any clinically relevant changes occurring during the study in the Event CRF. The investigator must determine whether an abnormal value in an individual study subject represents a

clinically significant change from the subject's baseline values. In general, abnormal laboratory findings without clinical significance (based on the investigator's judgment) are not to be recorded as adverse events. However, laboratory value changes that require treatment or adjustment in current therapy are considered adverse events. Where applicable, clinical sequelae (not the laboratory abnormality) are to be recorded as the adverse event.

All protocol-required laboratory assessments, as defined in [Appendix 2](#), must be conducted in accordance with the laboratory manual and the Schedule of Activities.

9.2.4.1 Human Immunodeficiency Virus (HIV) Status

Human immunodeficiency virus antibody titers will be assessed as specified in the Schedule of Activities. The result must be negative and will be documented in the source document but will not be recorded on the eCRF.

9.2.4.2 Hepatitis B and C Status

The following should be followed for the determination of hepatitis B and C status:

- if hepatitis B and/or hepatitis C status is known to be positive by serology no additional laboratory testing procedures are required
- if hepatitis B and/or hepatitis C status is not known to be positive by serology, the following laboratory testing is required:

Hepatitis B surface antigen

- if results are hepatitis B surface antigen positive, no additional testing is necessary

Hepatitis B Core Antibody

- if results are hepatitis B core antibody positive but negative for hepatitis B surface antigen, additional testing is necessary for hepatitis B virus DNA by polymerase chain reaction

Hepatitis C virus antibody

- if results are hepatitis C virus antibody positive, no additional testing is necessary.

9.2.4.3 Tuberculosis Testing

All subjects must receive either a PPD, Quantiferon, or T-SPOT test at screening.

9.2.4.3.1 Purified Protein Derivate (PPD)

The PPD test must be read by a trained healthcare professional 48 to 72 hours after the test is placed. PPD reader must be identified on the delegation of authority for this

responsibility. PPD test kits will not be provided by the sponsor and must be procured locally.

9.2.4.3.2 Quantiferon or T-SPOT Testing

If a subject does not receive a PPD test they must have Quantiferon or T-SPOT testing per [Section 6.2](#). If testing is performed by central laboratory then refer to the central laboratory manual for instructions on sample collection, processing, and shipping of samples.

9.2.4.3.3 Chest Radiograph

Subjects with a positive PPD test without a history of *Bacillus Calmette-Guerin* vaccination or subjects with a positive or indeterminate Quantiferon or T-SPOT test will require a chest radiograph including posterior-anterior and lateral views performed within 3 months before the first dose of investigational product. The radiograph report should be read by a radiologist or per local requirement and the report must be reviewed by the investigator before enrollment of the subject.

9.2.4.4 Pregnancy Testing

A high sensitive (serum) pregnancy test should be completed at screening for females of childbearing potential.

Note: Females who have undergone a bilateral tubal ligation/occlusion should have pregnancy testing per protocol requirements. (If a female subject, or the partner of a male subject, becomes pregnant it must be reported on the Pregnancy Notification Worksheet, see [Figure 12-2](#)). Refer to [Appendix 5](#) for contraceptive requirements.

For women of childbearing potential, additional urine pregnancy testing should be performed at monthly intervals during treatment with efavaleukin alfa and 6 weeks (\pm 3 days) after the last dose of protocol-required therapies. On visits where required, urine pregnancy tests must be given prior to dosing with investigational product. If a urine pregnancy test is positive, investigational product must be withheld; if pregnancy is confirmed, then investigational product must be discontinued.

Additional on-treatment pregnancy testing may be performed at the investigator's discretion or as required per local laws and regulations.

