Clinical Chemistry and Hematology								X							X													X	X	X
Pregnancy Test ^f								X							X													X	X	X

Page 1 of 2

Footnotes are defined on the last page of the table.

Table 2-4. Phase 1b Schedule of Activities – Extended Dosing Period Subjects Only (Week 105 Through Week 158)

	Visits for weekly dosing	TREATMENT PERIOD ^a																											PD Visit	SFU/ EOS ^b				
		Visits for weekly and biweekly dosing																																
Study Week	105,107,109,111, 113,115,117,119, 121,123,125,127, 129,131,133,135, 137, 139, 141, 143, 145,147,149,151, 153,155,157	106	108	110	112	114	116	118	120	122	124	126	128	130 ^c	132	134	136	138	140	142	144	146	148	150	152	154	156	158	Any-time					
PHARMACOKINETIC AND ANTIBODY ASSESSMENTS																																		
OTHER																																		
Lymphocyte Subsets ^k																																		
Biomarker Development Sample ^k																																		
DOSE																																		
Weekly Efavaleukin Alfa Administration ^l		X	X	X	X	X	X	X	X	X	X	X	X	X	X	X	X	X	X	X	X	X	X	X	X	X	X	X	X	X				
Biweekly Efavaleukin Alfa Administration ^l			X	X	X	X	X	X	X	X	X	X	X	X	X	X	X	X	X	X	X	X	X	X	X	X	X	X	X	X				

Page 2 of 2

CRF = case report form; cGVHD = chronic graft versus host disease; ECG = electrocardiogram; EOS = end of study for individual subject; EOET = end of extended treatment; GVHD = graft versus host disease; NIH = National Institutes of Health; PD = progressive disease; PFT = pulmonary function test; PK = pharmacokinetics; Q2W = every 2 weeks; QW = every week; [REDACTED]; [REDACTED]; SFU = safety follow-up

Subjects in the extended dosing period who discontinue treatment prior to week 258 (Q2W dosing) or week 259 (QW dosing) for any reason will complete an EOET visit and 6-weeks of safety follow-up after the last dose of efavaleukin alfa. See [Table 2-6](#).

^a Subjects who withdraw early from treatment will complete the EOET visit and Safety follow-up visit within a window of \pm 7 days of the next regularly scheduled visit after the last dose of efavaleukin alfa, consisting of all assessments included in the week 260 visit.

^b Safety follow-up visit will be done 6 weeks (\pm 3 days) after the last dose of efavaleukin alfa. Women of childbearing potential will be required to complete a pregnancy test at this visit.

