^c Re-assessment of subject's response to efavaleukin alfa treatment will be conducted every 6 months and a decision may be made by the Sponsor, following discussion and agreement between the principal investigator and medical monitor, to allow subjects who wish to, to continue treatment through week 258 (Q2W dose) or week 259 (QW dose).

^d A single ECG will be collected prior to blood draws or other invasive procedures. See Section [9.2.3.3](#).

^e Record steroid use and/or changes to dose on concomitant medication CRF page.

^f A 2 or 6 minute walk test is optional for the NIH Form A assessment.

^g PFTs (spirometry) will be used in the NIH Form A assessment unless the subject is unable to comply. PFTs must be obtained at the Baseline visit unless they were performed at the Screening visit. Thereafter PFTs are strongly preferred at all visits which include the NIH Form A assessment and must be performed for all subjects who have an abnormal PFT at Baseline, who have known pulmonary GVHD or who have new pulmonary symptoms. If PFTs cannot be performed as part of the NIH Form A assessment, the lung symptom score should be substituted.

For women of childbearing potential, on study pregnancy tests are urine.

^h Doses of investigational product in phase 1b must be given within \pm 3 days from the scheduled visit for subjects in Q2W dosing and \pm 2 days from the scheduled visit for QW dosing. Subjects will remain at the site for at least 30 minutes following doses of investigational product. Once [REDACTED] has been selected, investigational product will be administered within \pm 2 days.

Table 2-5. Phase 1b Schedule of Activities – Extended Dosing Period Subjects Only (Week 159 Through Week 222)

	Visits for weekly dosing	TREATMENT PERIOD ^a																									PD Visit	SFU/ EOS ^b			
		Visits for weekly and biweekly dosing																													
Study Week	159,161,163,165, 167,169,171,173, 175,177,179,181, 183,185,187,189, 191,193,195,197, 197,199,201,203, 205,207,209,221	160	162	164	166	168	170	172	174	176	178	180	182 ^c	184	186	188	190	192	194	196	198	200	202	204	206	208 ^c	210	222	Any-time		
GENERAL ASSESSMENTS																															
Physical Examination																														X	
Vital Signs	X	X	X	X	X	X	X	X	X	X	X	X	X	X	X	X	X	X	X	X	X	X	X	X	X	X	X	X	X		
Weight																		X											X		
ECG ^d																		X											X	X	
CLINICAL OUTCOME ASSESSMENTS																															

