- 216 Phase 1b subject is unable to avoid alcohol during the 4-week DLT evaluation period or tobacco consumption for the duration of the study.
- 217 Subject has known sensitivity to efavaleukin alfa or its excipients to be administered during dosing.
- 218 Subject likely to be unable to complete all protocol-required study visits or procedures, and/or to comply with all required study procedures (eg, Clinical Outcome Assessments [COAs]) to the best of the subject and investigator's knowledge.
- 219 History or evidence of any other clinically significant disorder, condition, or disease (with the exception of those outlined above) that, in the opinion of the investigator or Amgen physician, if consulted, would pose a risk to subject safety or interfere with the study evaluation, procedures, or completion.
- 220 Females who are pregnant or breastfeeding, or planning to become pregnant or breastfeed during treatment and for an additional 6 weeks after the last dose of efavaleukin alfa.
- 221 Females of child-bearing potential with a positive pregnancy test (assessed by a serum pregnancy test at screening and a urine pregnancy test at baseline).
- 222 Females of childbearing potential who are unwilling to use 1 highly effective method of contraception during treatment and for an additional 6 weeks after receiving the last dose of efavaleukin alfa. Refer to [Appendix 5](#) for additional contraception information.
- 223 Subject has previously entered this study.

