8.3 Lost to Follow-up

A subject will be considered lost to follow-up if he or she repeatedly fails to return for scheduled visits and is unable to be contacted by the study site.

The following actions must be taken if a subject fails to return to the clinic for a required study visit:

- The site must attempt to contact the subject and reschedule the missed visit as soon as possible and counsel the subject on the importance of maintaining the assigned visit schedule and ascertain whether or not the subject wishes to and/or is able to continue in the study.
- In cases in which the subject is deemed lost to follow-up, the investigator or designee must make every effort to regain contact with the subject (where possible, 3 telephone calls and, if necessary, a certified letter to the subject's last known mailing address or local equivalent methods). These contact attempts are to be documented in the subject's medical record.
- If the subject continues to be unreachable, he/she will be considered to have withdrawn from the study with a primary reason of lost to follow-up.

- For subjects who are lost to follow-up, the investigator can search publicly available records [where permitted]) to ascertain survival status. This ensures that the data set(s) produced as an outcome of the study is/are as comprehensive as possible.

9. Study Assessments and Procedures

Study procedures and their time points are summarized in the Schedule of Activities (see [Table 2-1](#), [Table 2-2](#), [Table 2-3](#), [Table 2-4](#), [Table 2-5](#), [Table 2-6](#), [Table 2-7](#), and [Table 2-8](#)).

As protocol waivers or exemptions are not allowed if an enrolled subject is subsequently determined to be ineligible for the study, this must be discussed with the sponsor immediately upon occurrence or awareness to determine if the subject is to continue or discontinue study treatment.

Adherence to the study design requirements, including those specified in the Schedule of Activities, is essential and required for study conduct.

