## **1. Introduction**

The purpose of this Statistical Analysis Plan (SAP) is to provide details of the statistical analyses that have been outlined within the protocol for study 20160283, efavaleukin alfa dated 22 June 2021. The scope of this plan includes the analysis that is planned for phase 1b part and will be executed by the Global Biostatistical Sciences (GBS) department unless otherwise specified. Analyses described in the protocol for the phase 2 part will not be conducted as the study is being terminated early.

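### Protocol Section 9.2.4.4 requires monthly urine pregnancy tests throughout treatment, but the legible pregnancy-test rows of Tables 2-4 to 2-6 (weeks 105 to 260) are well short of monthly

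*Protocol*

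**What the plan says.** Protocol Section 9.2.4.4 sets the frequency: "additional urine pregnancy testing should be performed at monthly intervals during treatment with efavaleukin alfa", plus one test 6 weeks after the last dose. It makes no exception for the extended dosing period, which can run to week 258 (every-2-week dosing) or 259 (weekly dosing). A positive urine test means the product is withheld, and a confirmed pregnancy means it is stopped. The section also allows more testing: "Additional on-treatment pregnancy testing may be performed at the investigator's discretion or as required per local laws and regulations". That adds to the monthly rule and does not relax it.

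The Schedule of Activities (Section 2.2) has a row labelled "Pregnancy Test" in each table. Footnote b of Tables 2-4, 2-5 and 2-6 covers the safety follow-up visit: "Women of childbearing potential will be required to complete a pregnancy test at this visit". The other legible pregnancy footnote in these tables concerns the specimen only: "For women of childbearing potential, on study pregnancy tests are urine".

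The opening of Section 9 makes the schedule binding: "Adherence to the study design requirements, including those specified in the Schedule of Activities, is essential and required for study conduct".

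**The concern.** Two parts of one protocol give different testing frequencies for the same women. After week 104 the schedule appears to drop to a handful of pregnancy tests per table, while the text still asks for one a month. Sites usually work from the schedule tables, and Section 9 tells them to adhere to those tables.

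A site that did only what Tables 2-4 to 2-6 mark would go much longer than a month between tests in women still dosed every 1 or 2 weeks. Because the test gates dosing, a longer interval means that an unrecognised pregnancy could be exposed to more doses before the product is withheld. The same site would also be departing from Section 9.2.4.4. What is at stake is participant safety and protocol consistency, not inference.

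**Working it through.** The plan gives no total number of tests, so there is no figure of its own to reproduce. The check compares the legible marks in each row with the number that monthly testing implies.

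**Inputs.** The week spans come from the table titles in Section 2.2. The marks are counted in the pregnancy and the chemistry/hematology rows. "Monthly" is read in two ways: every 4 weeks (weeks ÷ 4), or calendar months (weeks × 7 ÷ 30.44 days).

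| Table | Weeks | Length | ÷ 4 | × 7 ÷ 30.44 | Pregnancy marks | Chemistry marks |
|---|---|---|---|---|---|---|
| 2-4 | 105–158 | 54 | 13.5 | 12.4 | 5 | 5 |
| 2-5 | 159–222 | 64 | 16.0 | 14.7 | 5 | 5 |
| 2-6 | 223–260 | 38 | 9.5 | 8.7 | 5 | 5 |
| Total | 105–260 | 156 | 39.0 | 35.9 | 15 | 15 |

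**Reading the counts.**

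1. Counting every legible mark in the three pregnancy rows gives 5 + 5 + 5 = 15, against about 36 to 39.
2. Not all 15 are on-treatment tests. Footnote b places a test at safety follow-up in each table, and some marks appear to belong to the progressive-disease visit. The comparison in step 1 is therefore generous to the schedule.
3. Table 2-3 (weeks 53–104) is a useful contrast. Its pregnancy row shows 13 marks, one in every second 2-weekly column. Monthly testing over 52 weeks needs 52 ÷ 4 = 13, or 52 × 7 ÷ 30.44 = 12.0. Even if one of the 13 is the follow-up test, the row fits a 4-weekly schedule. So a monthly pattern remains visible in the extracted text in the one table where it most clearly appears.
4. In each of Tables 2-4 to 2-6 the chemistry row also has five marks, in the same or a similar pattern. Random loss of marks would be unlikely to thin two rows alike in three tables. A lighter visit schedule after week 104 is a more natural explanation.
5. No legible footnote to these tables states a lower pregnancy-test frequency, and Section 9.2.4.4 has no clause for weeks 105 onwards. The Amendment 5 rationale says that this amendment added the dosing beyond week 104, so the general section may simply not have been reconciled with the new tables. That is an inference; the documents do not say so.

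**The case against.** **The tables are damaged.** This is the strongest objection, and much of it stands. In Table 2-4 the lymphocyte and biomarker rows are empty and several other rows are missing, although their footnotes survive. Its pregnancy row cites a footnote letter that belongs to the walk test. The re-assessment footnote sits on week 130, while the nearby weight mark reads as week 132. Table 2-5's header jumps from week 210 to 222. Table 2-6's header omits week 238, and its pregnancy row has more cells than the header. Table 2-2's pregnancy row reads as roughly every 2 weeks after week 18, which is not monthly either. There are also redactions around the Table 2-5 pregnancy footnote.

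From the column positions in Table 2-4 a reader might infer tests at weeks 118, 132 and 158, with gaps of 14 and 26 weeks. The reader might then go on to a percentage of required tests, an upper limit, or a count of tests to be added. The documents do not support that precision. Matching cell counts do not show that every mark in a row survived or sits in its true column.

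**The text already governs.** A site can meet both texts by testing monthly, and the tables do not forbid it. This also stands: the tables and the text can be reconciled, and harm requires a site to overlook an explicit section. But when the protocol itself calls adherence to the schedule essential, a schedule that shows fewer tests invites that oversight.

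**Few women are affected.** They must respond, be approved past week 104, and not have been excluded as "unwilling to use 1 highly effective method of contraception during treatment". The SAP adds that "the study is being terminated early". This limits the severity but does not remove the inconsistency.

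**Conclusion.** The inconsistency holds, as a minor one. Section 9.2.4.4 requires monthly urine tests for as long as efavaleukin alfa is given. The legible schedule for weeks 105 to 260 shows five marks per table, follow-up included, which is well short of monthly and looks roughly quarterly or sparser. This rests on two assumptions: that extraction did not remove most of the marks from these rows, and that no redacted footnote restores monthly testing. The matching chemistry rows and the intact 4-weekly row in Table 2-3 make the first reasonable; the second cannot be checked.

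A reader might also infer that the tables override the monthly rule, or that the sponsor meant to relax it. The documents do not settle which text reflects the intent. No endpoint, analysis set or planned analysis depends on the answer.

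**What to change.** Add one footnote to the pregnancy-test rows of Tables 2-4, 2-5 and 2-6, requiring a urine test at monthly intervals per Section 9.2.4.4 while efavaleukin alfa is being given, before dosing where a dose is due. Equivalently, mark the test about every 4 weeks at existing visits. If a longer interval after week 104 was intended, Section 9.2.4.4 should instead state and justify it.

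The editing cost is one footnote or three table rows. The participant cost is a few more urine tests than the tables show for the few women of childbearing potential treated past week 104. These tests are already required by the text and can be done at visits already held every 1 to 2 weeks. No analysis needs to change.
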